4.12.3. Evaluation of IM Impact on PK, PD, Efficacy and Safety

The impact of IM on PK, PD, and safety will be evaluated by stratifying plasma trough and post-treatment ISIS 721744 concentrations, PD biomarker levels, selected clinical efficacy end points and safety measures by subject ADA status, summarized using typical descriptive statistics, and presented graphically and/or in tables. Efficacy and PD measures to be stratified by subject IM status may include Investigator-confirmed HAE attacks and plasma PKK levels . Safety measures to be stratified by subject IM status may include AEs, and lab tests for

TP-GDO-WW-016-08 CONFIDENTIAL Project Document Version No. 2.0 Effective Date: 26 Nov 19 Project Document Effective Date: 13 Dec 2023 Related to: SOP-GDO-WW-019 Page 47 of 61

hematology, liver and kidney functions. Other efficacy, PD and safety measures stratifications with subject IM status may also be conducted, if deemed appropriate.

Other stratifications (e.g., based on antibody titer, onset of ADA, etc.) of selected PK, PD, efficacy and safety assessments may also be performed if deemed warranted at the discretion of the pharmacokineticist, medical monitor, and/or biostatistician.

4.13. Exploratory Analyses

All exploratory analyses will be performed as a reference based on the FAS as defined in Section 4.5. By-patient listings will be provided too. Missing data will not be imputed.

For exploratory endpoints which are count data, in the case when Poisson regression models cannot be converged, e.g., when all patients within one treatment group have 0 event, Fisher's Exact Test will be used as the main analysis.

For exploratory endpoints which are responder data, in the case when Logistic regression models cannot be converged, e.g., when all patients within one treatment group are responders, Fisher's Exact Test will be used as the main analysis.

In the case of convergence problems with the repeated measures mixed model, Section 4.9.3.7 provides alternative model options.

4.13.1. Change and Percent Change from Baseline in Plasma Prekallikrein (PKK) Level

The change and percent change from baseline in plasma PKK levels will be summarized by visit and treatment group. The change and percent change from baseline in plasma PKK levels at each visit during the treatment period will be compared between ISIS 721744 80 mg every 4 weeks (or every 8 weeks) and pooled placebo using MMRM model based on the FAS. The response variable is the change or percent change from baseline at post-baseline visit up to Week 25.

The MMRM model will include effects of treatment, time, treatment-by-time interaction, and baseline value. The unstructured covariance model will be used to model the within patient errors, shared across treatment and small sample adjustments to standard errors and tests will be made following the Kenward-Roger approach (Kenward and Roger 1997).

4.13.2. Change from Baseline in Generalized Anxiety Disorder (GAD-7) Questionnaire Total Score

A GAD-7 questionnaire will be administered to evaluate anxiety experienced by patients. The GAD-7 is a self-administered patient questionnaire and it is used as a screening tool and severity measure for generalized anxiety disorder (Spitzer *et al.* 2006).

The GAD-7 questionnaire includes 7 questions, and the response to each question is scored as: Not at all = 0, Several days = 1, More than half the days = 2, Nearly every day = 3.

The total score is calculated by summing the score of each question and provides a possible score from 0-21. GAD-7 total score will be classified into severity stages (Spitzer *et al.* 2006) as shown below, which will be summarized for each visit.

TP-GDO-WW-016-08 CONFIDENTIAL Project Document Version No. 2.0 Effective Date: 26 Nov 19 Project Document Effective Date: 13 Dec 2023 Related to: SOP-GDO-WW-019 Page 48 of 61

Total Score Range	Symptom
0–4	Minimal Anxiety
5–9	Mild Anxiety
10–14	Moderate Anxiety
15–21	Severe Anxiety

The GAD-7 total score, the change and the percent change from baseline will be summarized by visit and treatment group. The change from baseline in GAD-7 total score will be compared between ISIS 721744 80 mg every 4 weeks (or every 8 weeks) and pooled placebo using the MMRM model based on the FAS. The MMRM model will include effects of treatment, time, treatment-by-time interaction, and baseline value. The unstructured covariance model will be used to model the within patient errors, shared across treatment and small sample adjustments to standard errors and tests will be made following the Kenward-Roger approach (Kenward and Roger 1997).

4.13.3. EuroQoL-5-Dimensions Quality of Life Questionnaire (EQ-5D-5L) and Change from Baseline in Visual Analog Scale (EQ VAS) Score

EQ-5D-5L is a standardized measure of health status developed by the EuroQoL Group to provide a simple, generic measure of health for clinical and economic appraisal (Herdman *et al.* 2011). The EQ-5D-5L consists of the EQ-5D-5L descriptive system and the EQ Visual analog scale (EQ VAS).

The EQ-5D-5L descriptive system comprises five dimensions (mobility, self-care, usual activities, pain/discomfort and anxiety/depression), and the response to each dimension is scored in 5 levels as: No problems = 1, Slight problems = 2, Moderate problems = 3, Severe problems = 4, Unable to/extreme problems = 5. Each state is referred to by a 5-digit code. For example, the health state, 12121, represents a patient who indicates no problems on mobility, usual activities, and anxiety/depression but slights problems on self-care and pain/discomfort.

EQ-5D health state index score reflects how good or bad a health state is according to the preferences of the general population of a country/region. To derive this index score, the response of each dimension from the EQ-5D-5L descriptive system will be first translated into a weight based on the value sets issued by EuroQoL group. Index value = 1 - sum of weights from these 5 dimensions' response.

The possible best value is 1 and the possible worst value varies by country. Validated weights for many countries are available from the EuroQol page of https://euroqol.org/support/analysistools/index-value-set-calculators/. If there is a missing response from a dimension, then the index value will not be calculated and be treated as missing. For countries without validated health state utility values yet, the suggestion from EuroQol group, currently, is using the United States EQ-5D-5L value set from (Pickard *et al.* 2019). The display of the index value is with 3 digits of decimal points.

The EQ VAS is used as a quantitative measure of health outcome as judged by the individual respondent. The EQ VAS records a self-rating of health status on a vertical VAS anchored at 100 (best imaginable health state) at the top and 0 (worst imaginable health state) at the bottom.

CONFIDENTIAL

TP-GDO-WW-016-08 Effective Date: 26 Nov 19 Related to: SOP-GDO-WW-019 **Project Document Version No.** 2.0 **Project Document Effective Date**: 13 Dec 2023

Project Document Effective Date: 13 Dec 2023 Page 49 of 61 The index score, its change and it's percent change from baseline as well as EQ VAS score, its change and it's percent change from baseline will be summarized by visit and treatment group. The change from baseline in index score and in EQ VAS will be compared between ISIS 721744 80 mg every 4 weeks (or every 8 weeks) and pooled placebo using the MMRM model based on the FAS. The MMRM model will include effects of treatment, time, treatment-by-time interaction, and baseline value. The unstructured covariance model will be used to model the within patient errors, shared across treatment and small sample adjustments to standard errors and tests will be made following the Kenward-Roger approach (Kenward and Roger 1997). Health state index score and EQ VAS will be summarized in tables and listed in a by-patient listing.

4.13.4. Patient Global Impression of Change (PGIC) Scale at Week 25/Early Termination

The PGIC scales will also be administered throughout the study for purposes of PRO validation and its use as an anchor for estimation of minimal important difference (MID) of other PRO measures. PGIC is a single item rated on a 5-point Likert scale (Much better = 1, A little better = 2, No change = 3, A little worse = 4, Much worse = 5) designed for patients to rate their own perceptions of change in HAE-related health status.

The number and percentage of patients of each scale at Week 25 will be summarized by treatment group.

The PGIC scale will be dichotomized to category of "better" and "no change or worse". The binary category data be summarized by treatment group and be analyzed by using a logistic regression. The odds ratio, corresponding 95% CI, and p-value will be provided.

The analysis will be conducted in FAS.

4.13.5. Change from Baseline in Patient Global Impression of Severity (PGIS) Scale

The PGIS scales will also be administered throughout the study for purposes of PRO validation and its use as an anchor for estimation of MID of other PRO measures. PGIS is a 1-item questionnaire rated on a 5-point scale (None = 1, Mild = 2, Moderate = 3, Severe = 4, Very severe = 5) designed to assess patient's impression of disease severity.

The number and percentage of patients of each scale will be summarized by visit and treatment group.

The change from baseline in PGIS will be summarized by visit and treatment group and be analyzed using Wilcoxon Sum Rank test.

The change from baseline in PGIS will also be dichotomized to category of "better" (change from baseline < 0) and "no change or worse" (change from baseline ≥ 0). The binary category data be summarized by visit and treatment group and be analyzed by using a logistic regression with baseline as the covariate.

Both analyses will be conducted in FAS.

TP-GDO-WW-016-08 CONFIDENTIAL Project Document Version No. 2.0 Effective Date: 26 Nov 19 Project Document Effective Date: 13 Dec 2023 Related to: SOP-GDO-WW-019 Page 50 of 61

4.13.6. Change from Baseline in Work Productivity and Impairment (WPAI)

Pharmacoeconomics will be assessed by the WPAI questionnaire plus Classroom Impairment Ouestions (CIO): specific health problem (SHP), US Version 2 (WPAI+CIO:SHP). Outcomes are expressed as impairment percentages, with higher numbers indicating greater impairment and less productivity, i.e., worse outcomes.

Questions:

During the past seven days (not including today, i.e., the day of answering questions):

- 1 = currently employed (No; Yes)
- 2 = hours missed work due to HAE symptoms
- 3 = hours missed work due to other reasons
- 4 = hours actually worked
- 5 =degree HAE symptoms affected productivity while working (0-10) with 0 =had no effect on my work and 10 = completely prevented me from working
- 6 = currently attended classes/school (No; Yes)
- 7 = hours missed classes/school due to HAE symptoms
- 8 = hours actually attend class or school
- $9 = \text{degree HAE symptoms affected productivity while in classes/school (0-10) with 0 = had no$ effect on my class work and 10 = completely prevented me from doing my class working
- 10 = degree health affected regular activities (0–10) with 0 = had no effect on my daily activities and 10 = completely prevented me from doing my daily activities

Weight of work/school for each subject and each visit per hours:

Weight of work (WW) = 0, if Q1 = No;
=
$$(Q2+Q3+Q4)/(Q2+Q3+Q4+Q7+Q8)$$
, if Q1 = Yes and Q6 = Yes;
= 1, if Q1 = Yes and Q6 = No;
Weight of school (WS) = 0, if Q6 = No;
= $(Q7+Q8)/(Q2+Q3+Q4+Q7+Q8)$, if Q1 = Yes and Q6 = Yes;
= 1, if Q1 = No and Q6 = Yes;

Weekly scores will be derived as following and multiply scores by 100 to express in percentages:

- Absenteeism Score is percent work/school time missed due to HAE symptoms: (Q2+Q7)/(Q2+Q3+Q4+Q7+Q8)
- Presenteeism Score is percent impairment while working/attending school due to HAE symptoms: $Q5/10 \times WW + Q9/10 \times WS$

TP-GDO-WW-016-08 **CONFIDENTIAL** Effective Date: 26 Nov 19 Related to: SOP-GDO-WW-019

• Overall Productivity Impairment Score is percent overall work/school impairment due to HAE symptoms:

• Activity Impairment Score is percent activity impairment due to HAE symptoms: O10/10

WPAI every-4-week mean score (WPAI4): Weekly WPAI score will be grouped into every-4-week intervals, incorporating WPAI+CIQ:SHP weekly scores from the 4 weeks immediately prior to/ at the assessment point. The mean of every-4-week WPAI score is to be calculated to get WPAI4. For example, WPAI4 at Week 5 is a mean of 4 consecutive weekly scores prior to Week 5 since Study Day 1. Similarly, each successive interval, i.e., WPAI4 at Week 9, Week 13, Week 17, Week 21 and Week 25, will start from the end of the prior interval, exclusively, and end 4 weeks later.

WPAI 4 of Absenteeism score, Presenteeism score, overall productivity impairment score and activity impairment score and the change from baseline will be summarized by visit and treatment group. Patients (or visits) with both Q1 = No and Q6 = No will be excluded from the summary of Absenteeism score, Presenteeism score and overall productivity impairment score.

All patients are expected to answer Q10 and have the activity impairment score. The change from baseline in WPAI4 of the activity impairment score will be compared between ISIS 721744 80 mg every 4 weeks (or every 8 weeks) and pooled placebo using the MMRM model based on the FAS. The MMRM model will include effects of treatment, time, treatment-by-time interaction, and baseline value. The unstructured covariance model will be used to model the within patient errors, shared across treatment and small sample adjustments to standard errors and tests will be made following the Kenward-Roger approach (Kenward and Roger 1997).

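### WPAI absenteeism in SAP 4.13.6 uses different denominators for work and school, and for patients who do both, the presenteeism weights count hours not worked or attended

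*Combined protocol and SAP*

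**What the plan says.** SAP 4.13.6 lists ten WPAI items and builds weekly scores from them.

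- **Absenteeism:** "Absenteeism Score is percent work/school time missed due to HAE symptoms: (Q2+Q7)/(Q2+Q3+Q4+Q7+Q8".
- **Items behind it:** Q2 is work hours missed for HAE, Q3 is "hours missed work due to other reasons", and Q4 is hours worked. On the school side, Q7 is "hours missed classes/school due to HAE symptoms" and Q8 is "hours actually attend class or school". No listed item records school time missed for any other cause.
- **Presenteeism:** "Presenteeism Score is percent impairment while working/attending school due to HAE symptoms", computed as Q5/10 × WW + Q9/10 × WS. Q5 is "degree HAE symptoms affected productivity while working (0-10", and Q9 is the same rating for class time.
- **Weights:** WW is 1 for a patient who is employed and not in school. WS is 1 for a patient in school and not employed. Only when both apply is WW set to the ratio "Q2+Q3+Q4)/(Q2+Q3+Q4+Q7+Q8", with WS = (Q7+Q8) over the same total.

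Weekly scores are averaged without weights into a 4-week mean (WPAI4). By visit and treatment group, the absenteeism, presenteeism, "overall productivity impairment score and activity impairment score and the change from baseline will be summarized". Only activity impairment (Q10) gets a mixed-model comparison. Patients or visits that are neither in work nor in school are left out of the work and school scores. Nothing is said about a zero denominator.

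**The concern.** The absenteeism score is presented as one quantity, but its denominator means different things in the two settings. For work it is all recorded hours, including those lost to leave or another illness. For school it is only the hours attended or lost to HAE. Protocol 5.1 admits patients from age 12, so students and workers will sit in the same arm summaries. A by-arm mean then depends partly on the mix of workers and students and on how much unrelated leave the workers took.

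The presenteeism point is narrower. The score is described as impairment during work or class, yet for patients who do both, the weights include hours when the patient was at neither. In the extreme case Q5 carries weight for a week with no hours worked.

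At stake are the descriptive productivity results and anyone's reading of them. No tested efficacy or safety conclusion depends on them.

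**Working it through.** The documents give no WPAI result, so there is no plan figure to reproduce. The formulas come from SAP 4.13.6. All hours and ratings below are illustrative assumptions.

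**1. Absenteeism in a single setting.**
Worker only (Q7 = Q8 = 0): Q2/(Q2+Q3+Q4).
Student only (Q2 = Q3 = Q4 = 0): Q7/(Q7+Q8).

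Take 40 scheduled hours with 8 lost to HAE, and vary the hours lost for other reasons. For the worker those hours go into Q3. For the student they are recorded nowhere and simply reduce Q8.

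| Hours lost otherwise | Worker | Student |
|---|---|---|
| 0 | 8/40 = 20.0% | 8/40 = 20.0% |
| 4 | 8/40 = 20.0% | 8/36 = 22.2% |
| 8 | 8/40 = 20.0% | 8/32 = 25.0% |
| 16 | 8/40 = 20.0% | 8/24 = 33.3% |

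In general, the worker's score is the student's score multiplied by (1 − Q3's share of all hours). In the 8-hour row, Q3 is 8/40 = 20% of hours, and 25% × 0.80 = 20%. Dropping Q3 from the worker's denominator reproduces the student column in every row.

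**2. Weeks with nothing due.**
A worker on leave all week (Q2 = 0, Q3 = 40, Q4 = 0) scores 0/40 = 0%, and that enters the 4-week mean. If the other three weeks average x, the mean becomes 0.75x. A student who answers yes to Q6 but has a week off (Q7 = Q8 = 0) gives 0/0, which the SAP does not address.

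**3. Presenteeism in a single setting.**
The weight is 1, so the score is Q5/10 or Q9/10 whatever Q2, Q3 and Q7 are. A rating of 5 gives 50% for a worker and 50% for a student. There is no discrepancy.

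**4. Presenteeism in both settings.**
The comparison uses hours actually worked or attended: WW = Q4/(Q4+Q8), WS = Q8/(Q4+Q8). Under either scheme the weights sum to 1, so

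SAP score − alternative = (WW under the SAP − Q4/(Q4+Q8)) × (Q5 − Q9)/10.

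The difference is zero when Q5 = Q9 and otherwise takes either sign.

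Assume 20 work and 20 school hours, with Q2 = Q7 = 0, Q3 = 10, Q4 = 10 and Q8 = 20. The SAP gives WW = 20/40 = 1/2. The alternative gives WW = 10/30 = 1/3.

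| Q5, Q9 | SAP | Hours worked or attended |
|---|---|---|
| 8, 2 | 50% | 0.8/3 + 0.2 × 2/3 = 40% |
| 2, 8 | 50% | 0.2/3 + 0.8 × 2/3 = 60% |
| 5, 5 | 50% | 50% |

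On a grid of 3,888 input combinations, the SAP score was above the alternative in 1,254, below it in 1,254 and equal in 1,380. The grid is symmetric in Q5 and Q9, so it shows that both directions occur and not how often each would in patients.

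In the extreme case Q3 = 20, Q4 = 0, Q8 = 20, the SAP gives Q5 half the weight although no hours were worked. With Q9 = 6, the score is 30% if Q5 is taken as 0, or missing if Q5 is blank. Class time alone gives 60%.

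**The case against.** **The work denominator can be defended.** The score can be read as a share of scheduled time. Then Q2+Q3+Q4 is a sensible work total, and 0% in a leave week is literally true, because HAE took no hours. This stands as a reason not to call Q3 an error in itself. It does not remove the mismatch: Q7+Q8 is not scheduled school time, because school hours missed for other causes are not recorded.

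**The scoring instructions are not in the documents.** They may prescribe a particular denominator. This stands, and no statement is made here about what they require.

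**Presenteeism is not diluted.** A reader might infer that presenteeism is pulled toward zero, or scored differently for workers and students. The documents do not support that. Patients in one setting get weight 1. For patients in both, the weights sum to 1, so weight only moves between Q5 and Q9.

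**Overall productivity score.** A reader might also extend the point to this score. Its formula is not readable in the available text, so nothing is claimed about it.

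**Large gaps need unusual weeks.** A worker at 20% against a student at 50% requires 24 of 40 hours lost for other reasons (8/40 against 8/16). With 4 such hours the gap is 20.0% against 22.2%. The loss of a quarter from a leave week assumes that week would otherwise have matched the other three.

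**Materiality is low.** This stands. SAP 4.13 treats the WPAI as exploratory, none of the 24 steps in SAP 4.9.1.4 is a WPAI score, and the modelled score uses Q10 alone.

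**Conclusion.** The point holds in two limited parts.

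First, the absenteeism formula treats work and school differently whenever Q3 is above zero. The worker's score is lower by a relative amount equal to Q3's share of hours: 20% against 25% when 8 of 40 hours are lost for other reasons, and no gap when Q3 = 0. The actual distribution of Q3 and the numbers of workers and students are not in the documents, so the effect on the arm summaries cannot be sized.

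Second, for patients who both work and study, the presenteeism weights do not match the score's own description. The error goes either way, vanishes when Q5 = Q9, and was 10 percentage points in the illustration. The number of such patients is not given.

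This is a low-priority correction to descriptive results.

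**What to change.** In SAP 4.13.6:

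- Score absenteeism as (Q2+Q7)/(Q2+Q4+Q7+Q8). With the listed items, this is the only denominator that can be computed the same way in both settings. If the sponsor prefers to keep Q3, the SAP should justify the difference between work and school.
- For patients who both work and study, use WW = Q4/(Q4+Q8) and WS = Q8/(Q4+Q8). Leave the weight of 1 for single-setting patients as it is.
- Set a weekly score to not applicable when its denominator is 0.
- Check all three against the scoring instructions of the WPAI version used, and cite them.

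The cost is a few formula lines in the SAP and the derivation program, and every item needed is already collected. After database lock, SAP Section 1 allows the change to be recorded in an SAP addendum or the clinical study report.

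There are two drawbacks. Weeks with no work or school due drop out, so the SAP should say how many valid weeks a WPAI4 needs. Weeks with few hours at risk can give extreme scores: Q2 = 8, Q3 = 32, Q4 = 0 moves from 8/40 = 20% to 8/8 = 100%, and such a week counts as much as a full one in the unweighted 4-week mean.

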4.13.7. Incidence of ER Visits, All-Cause Hospitalization, and Total Inpatient Days

The incidence of all-cause ER visits and ER visits due to HAE attack, all-cause hospitalization and total inpatient days during the treatment period will be summarized using descriptive statistics.

If supported by data, the incidence of all-cause ER visits, ER visits due to HAE attack and all-cause hospitalization may be compared between treatment group and pooled placebo group using a Poisson regression model and Pearson chi-square scaling of standard errors to account for potential overdispersion on the FAS. The model will include the treatment group as the factor. The logarithm of time in month that each patient observed during the on-treatment period will be used as an offset variable.

The total inpatient days may be compared between treatment group and pooled-placebo group using an ANOVA model with the treatment group as the factors.

4.13.8. Change in each AE-QoL Questionnaire Domain Scores

Scoring of each AE-Qol domain is described in the Section 4.9.3.7.

TP-GDO-WW-016-08 CONFIDENTIAL Project Document Version No. 2.0
Effective Date: 26 Nov 19 Project Document Effective Date: 13 Dec 2023
Related to: SOP-GDO-WW-019 Page 52 of 61

The change and percent change from baseline in each AE-QoL domain score will be summarized by visit and treatment group.

The change from baseline in each AE-QoL domain score at Week 13 and Week 25 will be compared between ISIS 721744 80 mg every 4 weeks and pooled placebo using the MMRM model. The MMRM model will include effects of treatment, time, treatment-by-time interaction, and baseline value at Study Day 1. Missing baselines will be imputed first by the average of available baselines across all patients in the FAS. The analysis will be conducted in the FAS. The unstructured covariance model will be used to model the within patient errors, shared across treatment and small sample adjustments to standard errors and tests will be made following the Kenward-Roger approach (Kenward and Roger 1997).

The comparison between ISIS 721744 every 8 weeks and pooled placebo will also be analyzed in the same way as above mentioned.

The least-squares means, standard errors, and the 2-tailed 95% confidence intervals for the treatment group and placebo group will be presented.

4.13.9. Time-Normalized Number of Investigator-Confirmed Hereditary Angioedema (HAE) Attacks (per Every-4-week) from Week 17 to Week 25

For exploring the dosing effect when administrated every 8 weeks with at least 3 doses of study drug, the time-normalized number of Investigator-confirmed HAE attacks (per every-4-week) from Week 17 to Week 25 will be analyzed using the same methods as described for the primary efficacy endpoint in Sections 4.9.2.1.

The analysis using Poisson regression model will be performed on a subset of FAS including patients in Cohort B who received ISIS 721744 and patients who received Placebo in both Cohort A and Cohort B.

For patients who discontinued the Treatment Period early and started OLE, and patients who discontinued the Treatment Period early and were lost to follow-up before Week 25, missing HAE count will be imputed by HAE count occurred during the last 56 days.

